1.2 Secondary Objectives

- Assess safety and tolerability of pregnenolone at the doses tested.
- Assess bioavailability of pregnenolone by demonstrating increases in serum pregnenolone and allopregnanolone levels with pregnenolone administration.
- Identify a dose of pregnenolone that demonstrates bioavailability, tolerability and that is associated with a significant change in a biosignature.

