Participants meeting the required inclusion criteria and none of the exclusion criteria, as determined by the PI or study clinician, will be randomized into the study. Any participants who sign a consent will be noted in the "Enrollment Log". If a participant is determined to be ineligible for the study post-consent, they will be considered a "screen fail" and an appropriate note will be made in the log.

Randomization will be performed by a statistician using a random number sequence (SAS Proc Plan). A randomization list will be maintained in a password protected folder by an unblinded staff member with no participant contact. In the R61 phase, a crossover design will be used so each participant will receive each of three study drug conditions in a random order. All tests will be 2-sided with p< 0.05 to assess significance.

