9.2 Sample Size and Randomization

Data from pooled randomized, controlled trials of how standard depression therapies influence proposed neuroimaging biosignatures (GABA) in a depressed population, and our rsFC connectivity data with pregnenolone, suggest that a sample size of n=31 would allow for > 25% attrition (higher than expected), and provide > 90% power with an α = 0.05 in the R61 phase of the experiment.(22) A sample size of 31 is adequate to detect within-group dose condition differences (500 mg vs. 800 mg vs. placebo) with an effect size (Cohen's d) of about 0.82 (medium to large) in the first phase. Thus, each pregnenolone dose will be compared to placebo separately. The reported d for changes in occipital GABA with depression treatment ranges from 1.28 to 1.59. The rsFC increase with pregnenolone, as compared to placebo, between the amygdala (seed region) and PCC in our pilot had an effect size of d = 3.28.

Randomization will be performed by an independent unblinded statistician (see Study Team Roster) not involved in data analysis prior to recruitment using a random number sequence (Statistical Analysis System [SAS] Proc Plan). A randomization list will be maintained in a password protected folder by an unblinded staff member with no participant contact. See section 6.2.3 Blinding for more information regarding the unblinding procedures.

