9.5.2 Secondary Outcomes

- **4. Tolerability.** Tolerability will be defined as no SAEs related to the study medication and no more than 10% of participants have a moderate or severe AE that is related to the product.
- 5. Bioavailability. Serum pregnenolone and allopregnanolone levels.
- 6. Dose of pregnenolone. Determine pregnenolone dose that demonstrates bioavailability, tolerability and that is associated with a significant change in a biosignature.

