To identify a dose of pregnenolone that demonstrates bioavailability, tolerability and that is associated with a significant change in a biosignature, a one-way repeated measure multivariate analysis of variance (MANOVA) with dose as a within subject variable and exit biosignature engagement and overall tolerability (as assessed by total SAFTEE scores) as outcome measures will be performed using the MANOVA statement in the PROC GLM function in SAS 9.4.

Additionally, the results from the R61 phase will be used to determine whether the trial progress to the R33 phase. Using the results of these analyses, go/no-go rules will then be applied to determine if the study progresses to the R33 phase. The "go" criteria will be defined as meeting 2 of 3 of the biological signatures, with a medium effect size (defined as Cohen's d \geq 0.5) in the proposed direction.

Go:

At least 2 of 3 biosignatures (amygdala-PCC, dIPFC-insula, occipital GABA concentration) achieve at least a medium effect size (defined as Cohen's d ≥ 0.5) in the proposed direction (increased rsFC with fMRI, increased GABA with MRS). Biomarkers were selected based on their relevance to depression, antidepressant response and postulated pregnenolone (or active metabolite) mechanism(s) of action. A detailed justification of the biosignatures with literature references is provided in the Research Strategy (section 3.3.e.)

- If more than one biosignature achieves the proposed effect size, then the project proceeds to the R33 phase and includes any biosignatures reaching the proposed effect size. Two of three biosignatures need to be in the proposed direction. If one or two of the biosignatures is on the opposite direction of prediction, then this will result in a "no-go" signal.
- The dose (500 mg/d or 800 mg/d) with a go on biosignature must show adequate tolerability. Tolerability will be defined as no SAEs related to the study medication and no more than 10% of participants have a moderate or severe AE that is related to the product.
- If both doses of pregnenolone achieve the go threshold, including having adequate tolerability, (on either the same or different biosignature) then the dose with the largest effect size on a biosignature (defined using Cohen's d) on a biosignature will be selected for the R33 phase.

No-go:

- None of the go rules are achieved.
- A biomarker(s) achieves proposed effect size, but in the opposite direction of prediction.

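### The MANOVA assigned to the dose-identification objective cannot show whether either dose meets it, and no stated analysis joins the objective's three conditions

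*Combined protocol and SAP*

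**What the plan says.** **The objective.** Section 1.2 sets it as: "Identify a dose of pregnenolone that demonstrates bioavailability, tolerability and that is associated with a significant change in a biosignature". Sections 3, 9.1 and 9.5.2 repeat the same three conditions.

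**The analysis assigned to it.** Section 9.6 (Pregnenolone Dose) names a one-way repeated-measures MANOVA in PROC GLM with dose as the within-subject variable. Its outcome list is "exit biosignature engagement and overall tolerability (as assessed by total SAFTEE scores) as outcome measures will be performed".

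**How the plan defines each condition elsewhere.**
- Bioavailability: section 1.2 speaks of "demonstrating increases in serum pregnenolone and allopregnanolone levels with pregnenolone administration", and section 9.5.2 names those two serum levels as the outcome. Section 9.6 analyses them by repeated-measures ANOVA with Tukey pairwise comparisons.
- Tolerability: section 9.5.2 requires no SAE related to study medication and "no more than 10% of participants have a moderate or severe AE that is related to the product". Section 9.6 repeats this under tolerability, under go and under no-go.
- Biosignature change: section 9.2 says "Thus, each pregnenolone dose will be compared to placebo separately", section 9.6 uses PROC MIXED with a Bonferroni correction, and section 4.3 adds "All tests will be 2-sided with p< 0.05 to assess significance".

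**The go rule (section 9.6).** At least 2 of the 3 biosignatures must "achieve at least a medium effect size", set at Cohen's d of 0.5 or more, in the proposed direction. Then: "The dose (500 mg/d or 800 mg/d) with a go on biosignature must show adequate tolerability". If both doses qualify, the larger biosignature d decides.

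**The concern.** The sentence in section 9.6 opens by restating the three-part objective and then names a test that covers one part as the plan defines it. Bioavailability appears in the stated purpose but not among the outcomes. The AE-based definition of tolerability is replaced by a self-report symptom total. The test compares all three conditions at once, so its p-value is not attached to either dose.

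At stake is whether a pre-specified objective has a pre-specified answer. As written, the way to combine the serum, AE and biosignature results for each dose would be settled after the treatment codes are opened. A dose could also be carried to R33 without its serum results having been part of the choice, although the objective makes them a condition.

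**Working it through.** This is mainly a check of text against text.

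**1. Which conditions does each stated analysis or rule cover?**

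| Analysis or rule | Serum levels | AE-based tolerability | Biosignature |
|---|---|---|---|
| MANOVA (dose objective) | no | no (SAFTEE total) | yes |
| PROC MIXED (primary aims) | no | no | yes |
| Tolerability definition and NLMIXED | no | yes | no |
| Bioavailability ANOVA with Tukey | yes | no | no |
| Mediation models (exploratory) | yes | no | yes |
| Go/no-go rule | no | yes | yes, by d of at least 0.5 |

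No row has three entries of yes. The go rule comes closest, with two that bear on a dose decision.

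**2. Can total SAFTEE stand in for the tolerability definition?** The definition is a count rule. With all 31 women exposed to a dose, 3/31 = 9.7% passes and 4/31 = 12.9% fails, provided there is no related SAE. With 25% attrition, 31 × 0.75 = 23.25, so about 23 women: 2/23 = 8.7% passes and 3/23 = 13.0% fails. A mean SAFTEE total carries neither the severity grade nor the judgement of relatedness, so it cannot tell 3 women from 4.

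**3. What does a significant MANOVA say?** The null hypothesis is that the whole vector of outcome means is equal under 500 mg, 800 mg and placebo. Rejecting it says that some outcome, or combination of outcomes, differs somewhere among the three conditions, in either direction. That is compatible with an effect at either dose or both, and in principle with a difference in SAFTEE alone. No follow-up contrast by dose is stated for this test.

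**4. Objective against go rule.**

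| Element | Objective | Go rule |
|---|---|---|
| Serum levels | required | absent |
| Standard for change | significant | d of at least 0.5 |
| Number of biosignatures | one | at least 2 of 3 |
| Tolerability | required | AE definition, by dose |

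A dose with one significant biosignature, with the other two below d = 0.5, satisfies the objective's biosignature condition and fails the go rule. A dose passing on 2 of 3 with good tolerability is a go whatever its serum results.

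**5. How far apart are significance and d of 0.5?** The plan states neither which d it means nor the Bonferroni divisor. Assume a within-person d and a paired t-test as an approximation to the PROC MIXED contrast. The smallest observed d that is significant is t(1 − 0.05/(2k), n − 1)/√n, where k is the divisor.

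| n | k = 1 | k = 3 (three biosignatures) | k = 6 (three biosignatures × two doses) |
|---|---|---|---|
| 31 | 2.042/√31 = 0.37 | 2.536/√31 = 0.46 | 2.825/√31 = 0.51 |
| 23 | 2.074/√23 = 0.43 | 2.591/√23 = 0.54 | 2.899/√23 = 0.60 |

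The two standards are not the same, but at the planned 31 women with the correction that the plan requires they lie close together (0.46 or 0.51 against 0.5).

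**The case against.** The strongest reply is that the pieces are all there. Section 9.2 promises each dose against placebo, section 9.6 gives biosignature contrasts and pairwise serum comparisons, and the AE definition is restated several times. The objective's own wording joins its conditions, so only one sentence applying it is missing. This stands in part: the shortfall is in the joining, and no new data or method is needed. It does not remove the problem, because section 9.6 is not silent here. It names a specific analysis for this objective, and that analysis does not answer it.

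Second, a percentage of participants cannot be a participant-level MANOVA outcome, so total SAFTEE may have been meant as a supplementary continuous measure. That is a fair reading. The plan does not say so, and it does not bring the AE definition into the answer to this objective.

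Third, the primary objectives are themselves framed around d of at least 0.5, so using that bar in a go rule is not an error. This also stands. The point is only that the objective and the go rule state different conditions.

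A reader might go further and infer that the MANOVA picks the R33 dose. It does not: the go rule does, by dose and with the AE definition. A reader might also infer that SAFTEE is likely to drive the MANOVA. Section 7.2 reports no side-effect difference from placebo at 100 and 500 mg/day in two earlier trials, so the documents give no ground for expecting that. It is a possibility of the test's form only.

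**Conclusion.** The plan is wrong as written for one secondary objective. The assigned MANOVA has no serum outcome, does not evaluate the plan's tolerability definition, and identifies no dose. None of the six analyses or rules in section 9.6 covers all three conditions. The go rule covers two, and it differs from the objective on the serum condition, on the standard for change and on the number of biosignatures.

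The core conclusion rests on the text and needs no numerical assumption. The comparison of significance with d of 0.5 assumes a within-person d, a paired-t approximation and divisors of 1, 3 or 6. It should not be read as evidence that the two standards would often disagree. At n = 31 with correction they nearly coincide, and the gap at n = 23 depends on attrition that section 9.2 calls higher than expected. The mismatches on serum levels and on one biosignature against 2 of 3 do not depend on those assumptions.

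The consequence is limited: the primary aims are untouched and the MANOVA does not decide progression. The point should be corrected before unblinding.

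**What to change.** In section 9.6, label the MANOVA supportive or exploratory, and answer this objective separately for each dose from results already planned:

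1. **Bioavailability:** serum pregnenolone and allopregnanolone against placebo, from the planned pairwise comparisons.
2. **Biosignature:** the dose-against-placebo contrasts from the primary PROC MIXED. The condition is met if at least one biosignature shows a Bonferroni-significant increase, with the divisor stated. The number follows the objective's wording and the direction follows the primary objectives.
3. **Tolerability:** the section 9.5.2 AE definition exactly as it stands, computed by dose with its denominator stated.

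Report a dose as meeting the objective only if all three hold, as the objective's own wording requires. Then reconcile the objective and the go rule on three matters: whether serum levels are a condition, significant change against d of at least 0.5, and one biosignature against 2 of 3. Which side should give way is for the sponsor; nothing here favours a dose or a clinical threshold.

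The cost is a short rewrite with the same data and software. The single omnibus p-value is no longer the analysis of this objective. How the early-dropout rule in section 9.3 should be read is a separate matter.

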Maximum time allowed between Visit 1 and Visit 2: 14 days (allow +/-3 day window for rescheduling). Participants will be instructed on when to begin their medication, such that the last dose (7th day) of the medication falls on the day of the MRI scan.

Visit 2 (~ 2.5 hours):

- Physician follow-up (includes review of concomitant medications and adverse events) – 20 minutes (done virtually or in person)
- Safety assessments: HRSD, SAFTEE, C-SSRS 30 minutes (done virtually or in person)
- Self-report: UCLA 5 minutes (done virtually or in person)
- Blood work for neurosteroid levels, vital signs, ECG 30 minutes
- MRI scan 1 hour

Maximum time between Visit 2 and Visit 3: 21 days (allow +/-5 day window for rescheduling)

Visit 3 (~ 40 minutes). Depending on the status of COVID-19, Visit 1 may be conducted virtually (to maintain safety precautions) or in person:

- Physician follow-up (includes review of concomitant medications and adverse events) – 20 minutes
- Safety assessments: HRSD 15 minutes
- At this visit (or within the allowable visit window) (and Visits 3 and 5), participants will begin a 7 day course of pregnenolone 500 mg, pregnenolone 800 mg, or placebo, which will be administered in a double-blind, crossover method. This

means that all participants will receive a 7 day exposure to each dose of pregnenolone and placebo throughout the study (each exposure will begin at Visit 1, 3, and 5); however, the order of treatment administration will be random. Each 7-day treatment administration will be followed by a 14 day washout period. (Example order: 800 mg x 7 days; washout x 14 days; placebo x 7 days; washout x 14 days; 500 mg x 7 days). If the visit is conducted remotely, the investigational drug will be mailed to the participant.

Maximum time between Visit 3 and Visit 4: 14 days (allow +/-3 day window for rescheduling). Participants will be instructed on when to begin their medication, such that the last dose (7th day) of the medication falls on the day of the MRI scan.

Visit 4 (~ 2.5 hours):

- Physician follow-up (includes review of concomitant medications and adverse events) – 20 minutes (done virtually or in person)
- Safety assessments: HRSD, SAFTEE, C-SSRS 30 minutes (done virtually or in person)
- Self-report: UCLA 5 minutes (done virtually or in person)
- Blood work for neurosteroid levels, vital signs, ECG 30 minutes
- MRI scan 1 hour

Maximum time between Visit 4 and Visit 5: 21 days (allow +/-5 day window for rescheduling)

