7.2 Methods and Timing for Assessing, Recording, and Analyzing Safety Parameters

Blood draw for CMP and CBC will be performed at Baseline and Visit 6. ECG will be done at Baseline, Visit 2, Visit 4, and Visit 6. Vital signs will be collected at Baseline and at each MRI scan. Urine pregnancy test (UPT) will be done at Baseline. If clinically

indicated, physical examination performed by a study clinician will be done at Baseline and Visit 6. An MRI screening form will be completed prior to each scan. A COVID-19 safety screener mandated by UT Southwestern will be done within 24-48 hours of each in-person visit.

In past two clinical trials (n=70 at 100 mg/day and n=80 at 500 mg/day) of pregnenolone in patients with Bipolar Disorder (BPD) or Major Depressive Disorder (MDD), no difference in side effect burden, as evaluated with a self-report side effect scale that assesses a variety of somatic symptoms, was observed with pregnenolone as compared to placebo. No adverse events classified as likely related to pregnenolone were observed in either study.

A clinical trial by Marx et al. in patients with schizophrenia (n=21) administered pregnenolone at the same dose as the current study (500 mg) and also reported excellent safety and tolerability in combination with psychotropic medications.(3) The only reported side effects with pregnenolone were mild restlessness, mild muscle pain or stiffness, and mild coldness in the extremities. No changes in TSH or blood glucose levels were observed with pregnenolone. Total cholesterol and LDL levels significantly decreased with pregnenolone, but the levels were not obtained in the fasting state. No ECG changes were observed. Lipids will be collected as part of the CMP panel to see if a reduction in LDL and total cholesterol can be replicated. ECG will be obtained as a precautionary measure, although changes are not anticipated. The GABAergic pregnenolone metabolite allopregnanolone has a benzodiazepine-like effect on sleep.(11) However, pregnenolone administration at the dosages that have been studied in humans do not appear to be associated with sedation or somnolence. Nonetheless, these symptoms will be monitored through both side effect and depressive symptom scales. There are no known drug-to-drug interactions with pregnenolone or its metabolites.

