7.3 Adverse Events and Serious Adverse Events

An **adverse event (AE)** is any untoward medical occurrence in a subject during participation in the clinical study or with use of the experimental agent being studied. An adverse finding can include a sign, symptom, abnormal assessment (laboratory test value, vital signs, electrocardiogram finding, etc.), or any combination of these regardless of relationship to participation in the study.

A serious adverse event (SAE) is one that meets one or more of the following criteria:

- Results in death
- Is life-threatening (places the subject at immediate risk of death from the event as it occurred)
- Results in inpatient hospitalization or prolongation of existing hospitalization
- Results in a persistent or significant disability or incapacity
- Results in a congenital anomaly or birth defect

An important medical event that may not result in death, be life threatening, or require hospitalization may be considered an SAE when, based upon appropriate medical judgment, the event may jeopardize the subject and may require medical or surgical intervention to prevent one of the outcomes listed in this definition.

During each study visit, participants will be asked to report any potential side effects and the SAFTEE score will be reviewed by a clinician. Abnormal blood panels and ECGs will be monitored by a clinician and repeated as needed. In addition, participants will be asked the general question "Has anything else felt different since

you started the study medication?" in order to capture unknown side effects or AEs. A clinician will meet with a study participant at each visit and document the occurrence of any potential side effects. The side effects will be classified using the Adverse Event grading scale as outlined in the DSMP. All AEs will be documented in both the participant chart and the REDCap data capture system.

An SAE can also meet criteria for an **Unanticipated Problem (UP)**. The Office for Human Research Protections (OHRP) considers unanticipated problems involving risks to subjects or others to include, in general, any incident, experience, or outcome that meets **all** of the following criteria:

- Unexpected in terms of nature, severity, or frequency given (a) the research procedures that are described in the protocol-related documents, such as the IRB-approved research protocol and informed consent document; and (b) the characteristics of the subject population being studied;

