9.3 Definition of Populations

The intent-to-treat (ITT) sample will be defined as follows: if a participant completes visits with at least one MRI scan, then useable data will be obtained. There is no baseline MRI, but only an MRI after each condition. Thus, having one scan will define ITT. In the case of early dropouts, the last data point collected will be entered into analyses for that participant (e.g. data on one dose condition but not all conditions).

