9.6 Data Analyses

Primary Aims:

To determine biosignature(s) sensitive to pregnenolone, scores on biosignatures will be compared between conditions using a random regression model with time and dose (500mg, 800mg, placebo) as within-subject factors using the PROC MIXED function. In determining statistical significance, Bonferroni corrections will be made to control for Type I error rates. Additionally, to explore the role neurosteroid levels have in the relationship between dose condition and biosignatures, separate mediational path models will be run. Specifically, following Preacher and Hayes' (2008)(26) bootstrap procedure, 5,000 bootstrap resamples will be examined using the Process macro (Hayes, 2013)(27) for SAS 9.4. In the path model, each biosignature will be regressed separately on to dose condition with neurosteroid levels included as a mediator (indirect effect). The following covariates will be included in this exploratory model: baseline scores on HRSD, age, depression severity, and depression duration.

95% confidence intervals will be examined and if the confidence interval does not contain zero, the effect will be considered statistically significant.

Secondary Aims: Tolerability

Tolerability will be defined as no SAEs related to the study medication and no more than 10% of participants have a moderate or severe AE that is related to the product. For dichotomous outcomes (e.g. drop out vs. completer) PROC NLMIXED will be used where dose and time will be added as within-subject factors and status as a dichotomous outcome variable.

Secondary Aims: Bioavailability

To assess **bioavailability** of pregnenolone and allopregnanolone, mean pregnenolone and allopregnanolone levels in each condition will be compared using a one-way repeated measures ANOVA. PROC ANOVA will be used to examine overall differences for each outcome, Bonferroni corrections will be made to control for Type I error rates, and Tukey's post hoc procedure will be used to examine pairwise comparisons for each condition.

Secondary Aims: Pregnenolone Dose

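### Section 9.6 analyses the SAFTEE total only jointly with biosignature engagement in a MANOVA, so it plans no dose-minus-placebo estimate for that score

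*Combined protocol and SAP*

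**What the plan says.** Safety and tolerability at the doses tested is a secondary objective (Section 1.2). The schedule in Section 6.1 has the SAFTEE at Visits 2, 4 and 6, which close the three treatment conditions, as well as at Baseline and the Safety Visit.

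Three parts of Section 9.6 touch tolerability:

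- **Tolerability.** This repeats the rule from Section 9.5.2: no related SAE, and "no more than 10% of participants have a moderate or severe AE that is related to the product". It then adds a model: "For dichotomous outcomes (e.g. drop out vs. completer) PROC NLMIXED will be used where dose and time will be added as within-subject factors".
- **Pregnenolone Dose.** A one-way repeated-measures MANOVA in PROC GLM, dose within subject, takes "exit biosignature engagement and overall tolerability (as assessed by total SAFTEE scores) as outcome measures". This is the only named analysis that uses the SAFTEE total. No contrast, estimate or interval for SAFTEE follows.
- **Go/no-go and dose choice.** These use Cohen's d on the biosignatures and the SAE/10% rule. SAFTEE does not appear.

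For serum levels, by contrast, the Bioavailability paragraph says that a Tukey "post hoc procedure will be used to examine pairwise comparisons for each condition".

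Section 9.3 defines the intent-to-treat sample by having at least one MRI scan. For early dropouts, "the last data point collected will be entered into analyses for that participant".

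**The concern.** The plan itself equates the SAFTEE total with overall tolerability, and the crossover yields that score on placebo and on both doses in the same woman. The natural summary is the within-woman difference of each dose from placebo. The MANOVA does not give it. It tests whether any of several responses differs by dose, so a significant result may come from connectivity or GABA alone, and a real SAFTEE change may be diluted by imaging responses that do not move.

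The other tolerability analyses answer different questions. The SAE/10% rule counts related moderate or severe events against a fixed limit. It has no placebo comparison and leaves out mild events, while the side effects the protocol expects (Sections 2.2 and 7) are all described as mild. The NLMIXED model is for yes/no outcomes.

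What is at stake is information rather than a decision. Section 7.2 cites the investigator's two earlier placebo-controlled trials for "no difference in side effect burden, as evaluated with a self-report side effect scale that assesses a variety of somatic symptoms". This trial extends the dose to 800 mg/d, and its Section 9 plans no stand-alone equivalent.

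**Working it through.** **1. The plan's own power figure.** Section 9.2 claims more than 90% power at d of about 0.82 with n=31 and over 25% attrition. A two-sided paired t-test at α=0.05 gives 99.3% at n=31 and 96.4% at n=23 (31 × 0.75 = 23.25). The claim reproduces, but it concerns biosignatures. No figure is stated for SAFTEE.

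**2. Assumptions.** The documents give no SAFTEE SD, effect size or correlation, and do not say how many responses make up biosignature engagement. For illustration, in units of the SD of the paired difference:

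- SAFTEE rises 0.25 at 500 mg and 0.5 at 800 mg;
- imaging is flat and uncorrelated with SAFTEE;
- the two dose-minus-placebo differences correlate 0.5.

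The data layout is not stated either, so both are shown.

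**3. Power to detect the SAFTEE change.** With one row per woman, the test is Hotelling's T² on p = 2 × (number of responses) differences, with F(p, n−p) and noncentrality n·μ′S⁻¹μ. Here μ = (0.25, 0.5) and S has unit variances and covariance 0.5, so μ′S⁻¹μ = (0.0625 − 0.125 + 0.25)/0.75 = 0.25. The noncentrality is 23 × 0.25 = 5.75 or 31 × 0.25 = 7.75. With one row per visit, Wilks' lambda was simulated (subject + dose model, 40,000 runs).

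| Responses tested | Per woman, n=23 / 31 | Per visit, n=23 / 31 |
|---|---|---|
| SAFTEE alone | 0.502 / 0.654 | 0.535 / 0.679 |
| SAFTEE + 1 biosignature | 0.360 / 0.508 | 0.416 / 0.556 |
| SAFTEE + 3 biosignatures | 0.221 / 0.340 | 0.298 / 0.412 |
| As above, SAFTEE correlating 0.3 with each biosignature | 0.300 / 0.466 | 0.406 / 0.562 |

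The last per-woman entry takes the biosignatures as mutually uncorrelated: 0.25/(1 − 3 × 0.09) = 0.342, so the noncentrality is 7.88 or 10.62. Correlation reduces the dilution.

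**4. Reverse case.** All three biosignatures move d=0.5 at both doses and SAFTEE is flat. Probability that the joint test is significant (per-visit figures from 20,000 runs):

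| Correlation between biosignatures | Per woman, n=23 / 31 | Per visit, n=23 / 31 |
|---|---|---|
| 0 | 0.781 / 0.948 | 0.906 / 0.980 |
| 0.3 | 0.541 / 0.771 | 0.697 / 0.860 |

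A positive MANOVA is therefore quite compatible with no SAFTEE change.

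**5. What a stand-alone contrast would give.** The 95% half-width is t(0.975, n−1)/√n: 2.042/√31 = 0.37 SD and 2.074/√23 = 0.43 SD of the paired difference. Paired t-test power for a 0.5 SD rise is 77% (n=31) or 63% (n=23). For a 0.25 SD rise it is 27% or 21%.

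**The case against.** The strongest reply is that no declared endpoint lacks an analysis. Section 9.5.2 defines tolerability by the SAE/10% rule, 9.6 applies it, and Section 7 gives SAFTEE a monitoring role. No decision would change. All of this stands. A reader might infer that the tolerability objective has no analysis, or that dose selection turns on a defective SAFTEE test. The documents support neither.

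A reader might also infer that nothing about side effects will be compared with placebo. That goes too far. The NLMIXED model includes dose, and its dropout example could extend to adverse-event occurrence, although not to a total score. Section 9.2 says that each dose will be set against placebo separately, but it does so among biosignature effect sizes. Section 7.3 says "The side effects will be classified using the Adverse Event grading scale as outlined in the DSMP"; that plan is not among the documents, so by-condition summaries there cannot be ruled out. PROC GLM may also print a univariate SAFTEE F-test, but 9.6 does not call for it, and an omnibus F is not an estimate against placebo.

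The power figures rest on assumed effects and an undefined number of imaging responses. With one biosignature the loss is smaller. They illustrate the point and do not establish it.

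Loss of SAFTEE scores through missing scans is a minor matter. Section 6.2.4 lists "Safety assessments: HRSD, SAFTEE, C-SSRS 30 minutes (done virtually or in person"), so a score can exist without a scan, but the same visit is built around the MRI. If 5% of scans were missing (an assumption; range 2–10%), the interval would widen by about 4% (2–9%) with one row per visit, the layout that Section 9.3 favours, or 9% (3–19%) with one row per woman.

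**Conclusion.** The point holds for the SAFTEE total in Section 9.6. The score is analysed only as a co-response with biosignature engagement, and that test cannot say whether SAFTEE moved, in which direction or by how much. The gap is visible in the text and does not depend on the assumed effect sizes. Under those assumptions, adding three flat biosignatures lowers power from 50–68% to 22–41% across both layouts and both sample sizes, and imaging alone makes the joint test significant in 54–98% of cases.

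The consequence is limited: the SAE/10% rule, the NLMIXED model, dose choice and go/no-go are untouched. It is a cheap improvement, held with medium confidence because the separate safety monitoring plan could not be seen.

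**What to change.** Under Tolerability in Section 9.6, add text to this effect:

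> The SAFTEE total at Visits 2, 4 and 6 will be analysed on its own with the PROC MIXED model specified for the biosignatures (time and dose within subject). The population is all women who received study drug and have a SAFTEE under at least one condition, whether or not a scan exists. The differences 500 mg minus placebo and 800 mg minus placebo will be reported with unadjusted 95% CIs as descriptive safety estimates. The MANOVA is supportive for SAFTEE.

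The population has to be named because Section 9.3 ties the only defined sample to having a scan. The word unadjusted is needed because the borrowed paragraph carries a Bonferroni correction. Leave the SAE/10% rule, dose choice and go/no-go criteria as they are.

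The cost is a few sentences and one extra model on data already collected. The drawback is precision: with half-widths of about 0.37 to 0.43 SD and only 21–27% power for a 0.25 SD rise, a null result cannot exclude a modest increase. A rise confined to one symptom could also be hidden in the total.
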